## 4 Study Objectives

### 4.1 Primary Objective

To determine the objective response rate (ORR) of tipifarnib in subjects with Head and Neck Squamous Cell Carcinoma (HNSCC) with HRAS mutations with a VAF $\geq$ 20% (High VAF population), as assessed by Independent Review Facility (IRF).

### 4.2 Key Secondary Objectives

To determine the ORR of tipifarnib in subjects with HNSCC with HRAS mutations of any VAF (All VAF population), as assessed by IRF.

To determine the Duration of Response (DOR) of tipifarnib in subjects with HNSCC with HRAS mutations with a VAF $\geq$ 20% (High VAF population), as assessed by IRF.

To determine the DOR of tipifarnib in subjects with HNSCC with HRAS mutations with any VAF (All VAF population), as assessed by IRF.

### 4.3 Other Secondary Objectives for AIM-HN

To determine the anti-tumor activity of tipifarnib in terms of progression free survival (PFS) and rate of PFS at 6 and 9 months in both the high VAF and all VAF populations.

To determine the anti-tumor activity of tipifarnib in terms of overall survival (OS) and rate of OS at 12 months in both the high VAF and all VAF populations.

Sponsor: Kura Oncology, Inc.  
Protocol no: KO-TIP-007

Statistical Analysis Plan  
Version 1.0 Date: 06-Jun--2023

[figure not shown]
To determine the anti-tumor activity of tipifarnib in terms of time to response (TTR) in both the high and all VAF populations.

To determine the anti-tumor activity of tipifarnib in terms of time to progression (TTP) in both the high and all VAF populations.

To investigate the safety and tolerability of tipifarnib according to the National Cancer Institute Common Terminology Criteria for Adverse Events version 5.0 (NCI CTCAE v5.0).

To investigate the effects of tipifarnib treatment on quality-of-life measures, including EORTC QLQ-H&N35 and EQ-5D-5L.

To assess population pharmacokinetics (PK) of tipifarnib in subjects with HNSCC with HRAS mutations.

[figure not shown]
## 5 Study Design

KO-TIP-007 is an international, multicenter, open-label, single-arm pivotal study, with two non-comparative sub-studies: (1) an interventional open-label, single arm, pivotal study evaluating the efficacy of tipifarnib in HRAS mutant HNSCC (AIM-HN) and (2) an observational study to evaluate the impact of HRAS mutations on response to first line systemic therapies for HNSCC (SEQ-HN).

[figure not shown]

**Figure 1. KO-TIP-007 Study Design**

### 5.1 AIM-HN Design

AIM-HN will enroll subjects with head and neck tumors of confirmed squamous histology with HRAS mutations. Subjects must have failed (e.g. tumor progression, clinical deterioration, or recurrence) their most recent prior therapy and at least one prior line of systemic therapy. See [Figure 2](#) for a depiction of the design of AIM-HN.

**Figure 2: AIM-HN Design**

All subjects must have measurable disease that meets the criteria for selection as a target lesion according to RECIST v1.1 and presence of at least measurable target lesion by local radiology prior to enrollment is required. HNSCC diagnosis will be by local laboratory. All AIM-HN enrolled subjects must have a known missense HRAS tumor mutation based on centralized testing or other HRAS test used by the trial site that has been approved by Kura Oncology, Inc.

AIM-HN enrolled subjects will receive treatment with tipifarnib until disease progression, unacceptable toxicity or any criteria for withdrawal from the trial or treatment occurs. Tipifarnib will be administered with food at a starting dose of 600 mg, orally, bid on days 1-7 and 15-21 of 28-day treatment cycles. Stepwise 300 mg dose reductions to control treatment-related, treatment-emergent toxicities may occur.

Tumor assessment for the primary analysis will be performed by IRF according to RECIST v1.1 and provided to the IDMB. Investigator assessment of tumor response will also be collected and reported as a supportive analysis. Tumor response assessment should occur approximately every 8 weeks ( $\pm 5$  days) for the first 12 months; thereafter, tumor response assessment should occur approximately every 12 weeks ( $\pm 5$  days) until disease progression. The tumor response assessment schedule (every 8-12 weeks) should be maintained regardless of dosing delays or additional imaging assessments performed. Upon disease progression, all subjects will be followed approximately every 12 weeks for survival and the use of subsequent therapy until either death or End of Study (up to 2 years after the enrollment of the last study subject, see [protocol Section 6.7.1](#)), whichever occurs first. All subjects will be followed-up for safety through the End of Treatment visit which occurs approximately 30 days after treatment discontinuation or immediately before the administration of another anticancer treatment, whichever occurs first. Additional safety follow-up may be conducted if unresolved toxicity is present at this End of Treatment visit.

[figure not shown]
## 5.2 SEQ-HN Design

SEQ-HN is an observational sub-study [REDACTED]

[REDACTED] See [Figure 3](#) for a depiction of the design of SEQ-HN. Demographics, disease history, information on prior anti-cancer treatments and

outcomes to prior treatments for HNSCC will be collected from all enrolled subjects. Approximately 225 control subjects with HNSCC without known HRAS mutation, will be enrolled into SEQ-HN. As part of their participation in SEQ-HN, subjects will be followed up through initiation of second line therapies, death, or consent withdrawn, whichever occurs first.

**Figure 3: SEQ-HN Design**

[REDACTED]

**5.4 Randomization**

KO-TIP-007 is a nonrandomized, open label study.

**6 Study Estimands**

Objectives	Estimands
Primary for AIM-HN	
To determine the objective response rate (ORR) of tipifarnib in subjects with Head and Neck Squamous	
 
Population of interest: mITT Analysis Set for subjects with High VAF
 
Variable/endpoint of interest: ORR by IRF
 

[REDACTED]

Sponsor: Kura Oncology, Inc.

Statistical Analysis Plan

Protocol no: KO-TIP-007

Version 1.0 Date: 06-Jun--2023

[figure not shown]
Cell Carcinoma (HNSCC) with HRAS mutations with a VAF $\geq$ 20% (High VAF population), as assessed by Independent Review Facility (IRF)	
Key Secondary for AIM-HN	
To determine the ORR of tipifarnib in subjects with HNSCC with HRAS mutations of any VAF (All VAF population), as assessed by IRF	
 
Population of interest: mITT Analysis Set
 
Variable/endpoint of interest: ORR by IRF
 

To determine the Duration of Response (DOR) of tipifarnib in subjects with HNSCC with HRAS mutations with a VAF $\geq$ 20%, as assessed by IRF	
 
Population of interest: mITT Analysis Set for subjects with High VAF and confirmed objective response (CR or PR)
 
Variable/endpoint of interest: DOR by IRF
 

To determine the DOR of tipifarnib in subjects with HNSCC with HRAS mutations of any VAF, as assessed by IRF	
 
Population of interest: mITT Analysis Set for subjects with confirmed objective response
 
Variable/endpoint of interest: DOR by IRF
 

Other Secondary for AIM-HN	
To determine the anti-tumor activity of tipifarnib in terms of progression free survival (PFS), and rate of PFS at 6 and 9 months in both the high VAF and all VAF populations	
 
Population of interest: mITT Analysis Set for subjects with High VAF/all VAF
 
Variable/endpoint of interest: PFS by IRF including the 6 month and 9 month progression-free rate
 

To determine the anti-tumor activity of tipifarnib in terms of overall survival (OS), and rate of OS at 12 months in both the high VAF and all VAF populations	
 
Population of interest: mITT Analysis Set for subjects with High VAF/all VAF
 
Variable/endpoint of interest: OS including the 12 month OS rate
 

To determine the anti-tumor activity of tipifarnib in terms of time to response (TTR) in both the high and all VAF populations	
 
Population of interest: mITT Analysis Set for subjects with confirmed objective response and High VAF/all VAF
 
Variable/endpoint of interest: TTR by IRF
 

To determine the anti-tumor activity of tipifarnib in terms of time to progression (TTP) in both the high and all VAF populations	This analysis is removed from the SAP

Sponsor: Kura Oncology, Inc.  
Protocol no: KO-TIP-007

Statistical Analysis Plan  
Version 1.0 Date: 06-Jun--2023

To investigate the safety and tolerability of tipifarnib according to the National Cancer Institute Common Terminology Criteria for Adverse Events version 5.0 (NCI CTCAE v5.0)
	
 
• Population of interest: Safety Analysis Set
 
• Variable/endpoint of interest: Incidence and severity of adverse events. Laboratory test results, Vital Signs and ECG results
 

To investigate the effects of tipifarnib treatment on quality of life measures, including EORTC QLQ-H&N35 and EQ-5D-5L
	
 
• Population of interest: mITT Analysis Set
 
• Variable/endpoint of interest: Changes in measures of quality of life using the following tools: EORTC QLQ-H&N35 and EQ-5D-5L
 

To assess population pharmacokinetics (PK) of tipifarnib in subjects with HNSCC with HRAS mutations
	
This analysis is removed from the SAP

## 7 Endpoints Definitions

In general, baseline is defined as the last measurement prior to the first dose of tipifarnib. If assessment time for an assessment on Cycle 1 Day 1 is missing, the assessment will also be considered baseline.

Change from baseline is defined as (value at post-baseline visit – value at baseline). In summary tabulations over time, unscheduled post-baseline values will be excluded unless otherwise stated.

For safety variables, on-treatment refers to the period from the start of study treatment through 30 days post treatment termination (last dose day).

## 7.1 Study Drug (Tipifarnib) Exposure Variables

### Duration of Exposure

Duration of exposure (months) is defined as (last dose date with >0 mg – first dose date + 1)/30.4375. Dosing start and end dates can be found on the Tipifarnib Dosing Log CRF pages.

### Number of Cycles Initiated

The number of cycles initiated where a dose > 0 mg was administered.

### Dose Interruptions

Dose interruptions and the reason for dose interruption will be summarized.

### Dose Adjustments

Dose adjustments of tipifarnib are captured as 'Dose Decreased Per Protocol', 'Dose Increased Per Protocol', 'Drug Interrupted', 'Drug Withdrawn' or 'Other' in the Dose Action field of the Tipifarnib Dosing Log CRF pages. Dose Interruptions and the reason for dose interruption will be summarized.

### Actual Cumulative Dose Administered

Actual Cumulative Dose administered (mg) is defined as the total amount of tipifarnib received as recorded in the "Actual Total Daily Dose" field on the Tipifarnib Dosing Log CRF pages, i.e., the sum of all doses administered over the periods indicated by the dosing start and stop dates.

### Relative Dose Intensity (RDI)

RDI (%) is defined as total dose taken by subject during exposure period divided by intended dose to be taken during exposure period.

$$\text{RDI (\%)} = 100 * (\text{Actual Dose Intensity}) / (\text{Intended Dose Intensity})$$

=  $100 * (\text{Actual Cumulative Dose}) / (\text{Intended Cumulative Dose})$  as the intended treatment duration is considered the same as the actual treatment duration for the Study drug

$$\text{Intended Cumulative Dose} = [(\text{Number of Cycles Initiated} - 1) \times 14 + \text{actual dosing days in the last cycle}] \times 600 \text{ mg} \times 2$$

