9.2.6 Tumor Response Assessment Visits

Tumor response assessment should occur approximately every 8 weeks (\pm 5 days) for the first 12 months of a subject's participation in AIM-HN; thereafter, tumor response assessment should occur approximately every 12 weeks (\pm 5 days) until disease progression. The tumor response assessment schedule (every 8 or 12 weeks) should be maintained regardless of dosing delays or additional imaging assessments performed.

The following procedures will be performed at this visit:

- Radiographic Imaging:
 - CT scan with a contrast agent is the preferred imaging method and the same technique should be used at baseline and post-treatment assessments. CT scan coverage should encompass scans of the neck (including the skull base), chest and abdomen (including

the liver and adrenals). Any other areas of disease involvement should be scanned based on the subject's signs and symptoms.

- Transfer of tumor scans and related clinical information to IRF

- [REDACTED]
- [REDACTED]
- [REDACTED]
- [REDACTED]
- [REDACTED]
- [REDACTED]
- [REDACTED]
- [REDACTED]
- [REDACTED]
- [REDACTED]
- [REDACTED]
- [REDACTED]
- [REDACTED]
- [REDACTED]
- [REDACTED]
- [REDACTED]
- [REDACTED]
- [REDACTED]
- [REDACTED]
- [REDACTED]
- [REDACTED]
- Concomitant medications
- Assessment of AEs
- [REDACTED]

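### The RDI formula leaves any wholly held cycle out of the intended dose, so two full cycles separated by a held cycle show 100% instead of 66.7%

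*SAP*

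**What the plan says.** Under Relative Dose Intensity in SAP 7.1: "RDI (%) is defined as total dose taken by subject during exposure period divided by intended dose to be taken during exposure period". The ratio of dose intensities is then reduced to a ratio of cumulative doses, "as the intended treatment duration is considered the same as the actual treatment duration for the Study drug". Intended Cumulative Dose is one less than the number of cycles initiated, times 14 days, plus the "actual dosing days in the last cycle", all times 1,200 mg per day (600 mg, twice).

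The cycle count is defined a few lines earlier: "The number of cycles initiated where a dose > 0 mg was administered". Duration of Exposure, also in SAP 7.1, runs by calendar from the first dose date to the last date with a dose above 0 mg, so gaps are inside it. That duration does not enter RDI.

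Protocol 9.2.6 anticipates that dosing may slip, since the tumour assessment schedule "should be maintained regardless of dosing delays or additional imaging assessments performed". SAP 9.4 reports RDI descriptively in the AIM-HN safety analysis set.

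**The concern.** The verbal definition and the formula do not describe the same quantity. Time cancels from the ratio only if the intended dose is what the schedule would have delivered over the actual treatment duration. The formula takes the intended dose from a count of cycles in which drug was given. A cycle with no drug lengthens the exposure period but leaves the intended dose unchanged.

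RDI is the one planned statistic in the visible text that sets dose delivered against dose intended. If held cycles vanish from it, a subject who went a whole cycle without drug is reported as having received the full intended dose, and the summary overstates how far the planned schedule was delivered.

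**Working it through.** The documents state no RDI value, so there is no figure to reproduce.

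**Inputs.** Planned schedule: Days 1–7 and 15–21 of 28-day cycles, 14 dosing days per cycle, 1,200 mg per day (SAP 5.1). RDI formula and cycle count: SAP 7.1. The dosing patterns below are assumed, with the full dose on every dosed day, so the 1,200 mg cancels and days suffice.

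**Formulas.**
- SAP: RDI = days taken / [(cycles with a dose − 1) × 14 + days dosed in the last cycle].
- Elapsed time: RDI = days taken / scheduled dosing days from first to last dose. Scheduled weeks start on days 1, 15, 29, 43, 57, 71 and so on.

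**Check on schedule.** Six full cycles on time: 84 / (5 × 14 + 14) = 84/84 = 100% by both formulas.

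**Cycle wholly held.** Doses on days 1–7, 15–21, 57–63 and 71–77; nothing on days 29–56.
- SAP: two cycles have a dose, so the denominator is 1 × 14 + 14 = 28 and RDI is 28/28 = 100%. The numbering is irrelevant. If numbering shifts, day 57 opens cycle 2. If cycles are fixed 28-day blocks, day 57 opens cycle 3, and cycle 2 is not counted because it has no dose.
- Elapsed time: six scheduled weeks to day 77, so 28/42 = 66.7%.

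**Shorter delay.** Doses on days 1–7, 15–21, 43–49 and 57–63 (14-day delay).
- SAP, numbering shifts: two cycles, 28/28 = 100%.
- SAP, fixed blocks: the doses fall in three blocks, the last with 7 dosed days, so the denominator is 2 × 14 + 7 = 35 and RDI is 28/35 = 80%.
- Elapsed time: five scheduled weeks to day 63, so 28/35 = 80%.

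| Pattern | SAP, numbering shifts | SAP, fixed blocks | Elapsed time |
|---|---|---|---|
| Two full cycles, one held cycle between | 28/28 = 100% | 28/28 = 100% | 28/42 = 66.7% |
| Six planned cycles, third held | 70/70 = 100% | 70/70 = 100% | 70/84 = 83.3% |
| Six planned cycles, third and fifth held | 56/56 = 100% | 56/56 = 100% | 56/84 = 66.7% |
| Two cycles, 14-day delay between | 28/28 = 100% | 28/35 = 80% | 28/35 = 80% |
| Four cycles, 14-day delay before each of cycles 2–4 (last dose day 147) | 56/56 = 100% | 56/77 = 72.7% | 56/77 = 72.7% |
| Six cycles, second dosing week of the third missed | 77/84 = 91.7% | 77/84 = 91.7% | 77/84 = 91.7% |

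The first three rows fail under either numbering. The next two fail only if numbering shifts. The last row shows that days missed inside a counted cycle before the last are captured correctly.

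**The case against.** A reader might infer that RDI is blind to every delay between cycles, and that it shows near-full intensity in the subjects who tolerated treatment worst. The documents do not support either reading.

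- **Delays.** The visible text does not say whether a late start shifts the cycle numbering, and the dose-modification section the protocol cites (8.1.2) is not in the public copy. The one visible cycle-day rule, SAP Table 2 for the quality-of-life windows, puts Day 1 of cycle n at 28 × (n − 1) + 1, a fixed grid. It does not govern the dosing log, but on such a grid the formula already captures the delays in rows four and five of the table. An estimate of bias built on shorter delays is therefore conditional.
- **Tolerability.** The denominator stays at 600 mg twice daily, so the stepwise 300 mg reductions lower RDI directly, as do days missed in counted cycles before the last.
- **Other outputs.** SAP 7.1 and 9.4 plan the number and percentage of subjects with an interruption or a dose decrease, with reasons, along with duration, cycles initiated, cumulative dose and a listing. Read together, these can reveal a gap.
- **Stakes.** RDI enters no estimand or efficacy analysis, and the SAP states its simplification openly.

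All of this stands as a limit on the point. None of it restores a held cycle to the denominator. An interruption count does not say how much time was lost, and a long duration beside few cycles does not correct the RDI figure.

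**Conclusion.** The formula is wrong as written for any cycle wholly without drug that is followed by a further dose. RDI then stays at 100% for a subject otherwise dosed in full, where the elapsed-time value in the examples is 66.7% to 83.3%, an overstatement of 16.7 to 33.3 points. This assumes only that the hold covers a whole cycle and that dosing resumes. For shorter delays the error depends on cycle numbering: 20 points in the 14-day example if a late start shifts the count, none if cycles are fixed blocks.

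The documents do not give the share of subjects with a held cycle. If it is a fraction f, and these examples are typical, mean RDI is overstated by 16.7f to 33.3f points: 1.7 to 3.3 points at f = 10%, and 3.3 to 6.7 points at f = 20%.

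The effect is confined to a descriptive exposure statistic. The change should be made, but the primary ORR result does not depend on it.

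**What to change.** In SAP 7.1, base Intended Cumulative Dose on elapsed time: the dosing days of the planned schedule from the first dose date to the last date with a dose above 0 mg, times 1,200 mg, with held cycles counted. Delete the statement that equates intended and actual treatment duration. If the present ratio is wanted, report it beside RDI under its own name, such as *dose compliance within started cycles*.

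A rigid grid from the first dose needs one refinement. Day 1 of later cycles has a ±2-day visit window (Protocol 9.2.4 and 9.2.5). If cycle 2 starts on day 27, its last dose falls on day 47, by which time the grid has scheduled 7 + 7 + 7 + 5 = 26 days, and RDI would be 28/26 = 107.7%. Shifts inside the window should therefore be treated as on time.

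Two consequences should be stated in the text. The new count also takes in days missed before the last dose within the final cycle, which the present formula does not charge. A hold that ends in discontinuation stays outside RDI, because the count stops at the last dose.

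The cost is a few lines of SAP wording, one derived variable from dates already on the dosing log, and a somewhat lower reported RDI. If the SAP is already final, its Section 2 provides for recording the deviation in the clinical study report.

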## 9.4 Extent of Study Drug Exposure

Exposure to study drug will be summarized in the AIM-HN safety analysis set. Descriptive statistics will be provided for duration of exposure, the total number of cycles initiated, actual cumulative dose administered, and Relative Dose Intensity.

The count and percentage of subjects with at least 1 dose interruption and at least 1 dose decreased per protocol will be presented along with a summary of the reasons for dose interruptions and dose decrease.

A listing of tipifarnib exposure will also be created.

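### The relative dose intensity formula drops whole scheduled days missed in the last cycle before the last dose, so it overstates RDI against the SAP's own definition

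*SAP*

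**What the plan says.** The Relative Dose Intensity entry in SAP 7.1 gives this definition: "RDI (%) is defined as total dose taken by subject during exposure period divided by intended dose to be taken during exposure period". It reduces RDI to actual over intended cumulative dose, on the ground that "the intended treatment duration is considered the same as the actual treatment duration for the Study drug". Intended cumulative dose is then computed as [(cycles initiated − 1) × 14 + "actual dosing days in the last cycle"] × 600 mg × 2.

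Four other places bear on this:

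- **Schedule (SAP 5.1):** dosing is "bid on days 1-7 and 15-21 of 28-day treatment cycles", which is 14 scheduled days per cycle. The same section notes: "Stepwise 300 mg dose reductions to control treatment-related, treatment-emergent toxicities may occur".
- **Exposure period (SAP 7.1, Duration of Exposure):** it runs by calendar from the first dose to the "last dose date with >0 mg", so gaps in dosing lie inside it.
- **Numerator (SAP 7.1, Actual Cumulative Dose Administered):** it is "the sum of all doses administered over the periods indicated by the dosing start and stop dates". A day with no drug adds nothing.
- **Reporting (SAP 9.4):** RDI is summarised descriptively. Separately, the number and percentage of subjects with "at least 1 dose interruption and at least 1 dose decreased per protocol will be presented", with reasons.

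**The concern.** The denominator uses two rules. For every cycle but the last it counts days planned. For the last cycle, on the plain meaning of the words, it counts days dosed. A whole scheduled day missed in the last cycle, with dosing resumed afterwards, therefore leaves both numerator and denominator, although it falls inside the exposure period to which the definition refers.

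The error always runs upward. For a subject otherwise at full dose, RDI stays at 100% despite the gap. After a shortfall in an earlier cycle, RDI falls too little. If the last cycle is at a reduced dose, RDI can rise when days are missed. Two subjects with the same total dose over the same period can get different values solely because of which cycle held the gap. What is at stake is the accuracy of one descriptive exposure measure.

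**Working it through.** The SAP gives no RDI value to reproduce, so the formula is compared with the SAP's own definition. The dosing patterns are assumed for illustration.

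**Inputs.** 14 scheduled days per cycle (SAP 5.1). Full daily dose 600 mg × 2 = 1,200 mg (SAP 7.1). Let k be the number of cycles initiated, A the days dosed in the last cycle, and P the scheduled days in that cycle up to the last dose.

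**Formulas.**
- SAP RDI = actual dose / {[14(k−1) + A] × 1,200}
- Planned-day RDI = actual dose / {[14(k−1) + P] × 1,200}
- Hence SAP RDI = planned-day RDI × [14(k−1) + P] / [14(k−1) + A], whatever the dose level or earlier shortfall.

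**Check.** With full compliance A = P = 14 and both give 100%.

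**Same dose, same period, gap in a different cycle.** Two cycles, days 2–7 missed in one of them, last dose on day 21 of cycle 2. Dose taken is 22 × 1,200 = 26,400 mg.

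| Gap in | SAP formula | Planned-day |
|---|---|---|
| Cycle 1 | 26,400/33,600 = 78.6% | 26,400/33,600 = 78.6% |
| Cycle 2 | 26,400/26,400 = 100% | 26,400/33,600 = 78.6% |

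**Earlier shortfall.** Cycle 1 dosed on 7 of 14 days and cycle 2 complete: 21/28 = 75.0%. With four days missed in cycle 2 before the last dose, dose taken is 17 × 1,200 = 20,400 mg. SAP: 20,400/(24 × 1,200) = 20,400/28,800 = 70.8%. Planned-day: 20,400/33,600 = 60.7%.

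**Reduced last cycle.** Cycle 1 complete and cycle 2 complete at 300 mg bid: (16,800 + 14 × 600)/33,600 = 75.0%. With four days missed in cycle 2, dose taken is 16,800 + 10 × 600 = 22,800 mg. SAP: 22,800/28,800 = 79.2%, a rise. Planned-day: 22,800/33,600 = 67.9%, a fall.

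**Size by number of cycles.** Six days missed in the last cycle (P = 14, A = 8):

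| k | Factor |
|---|---|
| 1 | 14/8 = 1.75 |
| 2 | 28/22 = 1.27 |
| 4 | 56/50 = 1.12 |
| 8 | 112/106 = 1.06 |

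**Where there is no discrepancy.** A subject at full dose who stops for good after day 7 of cycle 3: 42,000/42,000 = 100% both ways. Dose reductions, one missed dose of the two on a dosed day, and days missed in earlier cycles all still lower RDI under the SAP formula.

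**The case against.** The strongest reply is that the term is undefined, not wrong. The neighbouring definitions of exposure duration and cycles initiated restrict themselves explicitly to doses above 0 mg. That suggests the dosing log can hold 0 mg records, and interruption is one of its coded dose actions. The RDI term carries no such restriction. If it means log days including 0 mg rows, or scheduled days reached, the defect disappears. The SAP is to be read with a case report form that is not available here. This reading cannot be excluded, but it strains the ordinary meaning of the words, and nothing in the SAP states it. If it was intended, the term still needs a definition.

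The equal-duration convention does not help. It explains why days after permanent stopping are not charged, but the missed days in question lie inside the actual duration.

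Three further points stand:

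- The pattern is narrow: whole days missed, dosing resumed in the same cycle, and no later cycle begun.
- SAP 9.4 reports interruptions, decreases, cumulative dose and duration separately, although the interruption count does not measure dose lost against plan.
- The formula remains a cycle-count approximation after the correction. Take a subject dosed on days 1–7, 15–21, 43–49 and 57–63, with cycle 2 started 14 days late: 28/28 = 100%. Another, dosed on days 1–7, 15–21, 29–35 and 57–63 with three on-time cycles, gets 28/35 = 80%. Dose and period are the same, and the correction changes neither figure.

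**Conclusion.** The concern holds. On the plain reading of the last-cycle term, the formula departs from the SAP's own definition and overstates RDI whenever whole scheduled days are missed in the last cycle before the last dose. The factor is [14(k−1) + P] / [14(k−1) + A], largest when few cycles were given. This rests on taking the term to mean days on which drug was taken. The patterns shown are illustrative, and the documents give no frequency for them, so the effect on the trial's reported RDI is unknown. Importance is low: the measure is descriptive, and no efficacy result, test or analysis set depends on it.

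**What to change.** In the intended cumulative dose formula in SAP 7.1, replace the last-cycle term with *planned dosing days in the last cycle up to the last dose date*. Define this as the larger of (i) the scheduled days (1–7 and 15–21, counted from that cycle's actual Day 1) on or before the last dose date, whether or not dosed, and (ii) the days actually dosed, to a maximum of 14. Leave the numerator and the rest of the formula unchanged. If undosed scheduled days were always meant to count, this makes it explicit.

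Checks for a last cycle at full dose:
- Days 1–7 and 14–20 dosed: max(13, 14) = 14, so 16,800/16,800 = 100%. Scheduled days alone would give 16,800/15,600 = 107.7%.
- Days 1–7 and 17–23 dosed: 14/14 = 100%.
- Stopped for good after day 7 of cycle 3: still 100%.

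The cost is one redefined term, using dosing start and stop dates already on the dosing log. Reported RDI may be slightly less favourable. Late cycle starts are still not charged and must be read from the interruption summary. A late second dosing week that is then stopped part-way is charged for the delay: in a single cycle with days 1–7 and 17–19 dosed, 12,000/14,400 = 83.3%, against 100% under the present formula.
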